6.5 Randomization and Allocation Procedures

On the day of enrollment, subjects who meet the inclusion/exclusion criteria and whose parent / legally acceptable representative sign the ICF will be randomly assigned to Groups 1 through 4. Countries where PCV10 will be administered for pneumococcal vaccination, 1432 subjects will be randomized in a 1:1 ratio to 2 groups such that Groups 1 and 2 will have approximately 716 subjects each; and countries where PCV13 will be administered for pneumococcal vaccination, 220 subjects will be randomized in a 1:1 ratio to 2 groups such Groups 3 and 4 will have approximately 110 subjects each.

Randomization will be performed with permuted block method with stratification by center and age categories as follows: approximately 6 to 8 weeks (≥ 42 to ≤ 59 days), and 9 to 12 weeks (≥ 60 to ≤ 89 days).

^a All unexpected and related SAEs submitted to EU competent authorities must be unblinded.

The IRT system will also be used to allocate subjects in the rSBA subset in the countries included in the subsets as follows:

- 100 subjects randomized to Group 1; 100 subjects randomized to Group 2
- 50 subjects randomized to Group 3; 50 subjects randomized to Group 4

The rSBA subset will include subjects from all countries except Poland.

The vaccination / site staff will connect to the IRT system, enter the identification and security information, and confirm a minimal amount of data in response to IRT system prompts. The IRT system will then provide at least the vaccine dose number (except for the rotavirus vaccine) and subject number. The full detailed procedures for group allocation are described in the Operating Guidelines. If the subject is not eligible to participate in the study, then the information will only be recorded on the subject recruitment log.

Subject numbers that are assigned by the IRT system will consist of a 12-digit string (a 3-digit country identifier, a 4-digit study center identifier, and a 5-digit subject identifier). For example, Subject 724000100005 is the fifth subject enrolled in Center Number 1 in Spain (724 being the Spain country code).

Subject numbers should not be reassigned for any reason. The randomization codes will be kept securely in the IRT system.

6.6 Treatment Compliance

The following measures will ensure that the vaccine doses administered comply with those planned, and that any non-compliance is documented so that it can be accounted for in the data analyses:

- All vaccinations will be administered by qualified study personnel for pediatric population.
- The person in charge of product management at the site will maintain accountability records of product delivery to the study site, product inventory at the site, dose(s) given to each subject, and the disposal of unused or wasted doses

6.7 Concomitant Medications and Other Therapies

At the time of enrollment, ongoing medications including but not limited to other therapies (eg, blood products), should be recorded in the source documents. All new medications prescribed for new medical conditions / AEs during study participation should also be recorded in the source documents.

Documentation in the CRB of concomitant medication(s) will be limited to specific categories of medications (Categories 1, 2, and 3 as detailed below). Those will include Category 1, 2, and 3 medications ongoing at the time of inclusion in the study, or started at any time during the subject's participation in the trial. For category 3 medication, the period of reporting in CRB will be restricted to only 3 days (72 hours) prior to each blood sampling time point.

Collection period in source documents

Reportable medications (Category 1, 2, and 3) will be collected in the source documents from the day of first vaccination to the end of the trial.^a

Categories of Reportable medications and reporting period

Reportable medications include medications that impact or may impact the consistency of the safety information collected after any vaccination and/or the immune response to vaccination.

- Category 1: medications with potential impact on the evaluation of the safety of the study vaccines. For example, antipyretics, analgesics, non-steroidal anti-inflammatory drugs (NSAIDs), systemic corticosteroids (therapy duration less than 2 weeks), and other immune modulators. Category 1 medications do not define the Per-Protocol Analysis Set (PPAS).

Note: Topical steroids (Inhaled, otic, ophthalmic, nasal etc.) should not be captured or reported.

Category 1 medications will be reported in the CRB from the day of first vaccination to the end of the solicited and unsolicited follow-up period after each vaccination. These medications will also be collected in the CRB for the 30- day period prior to the subsequent doses of the vaccine, wherever applicable (second, third, fourth, etc., in case of a multi-dose schedule with more than a 30-day interval between doses).

- Category 2: Reportable medications with potential impact on immune response of the study vaccines and used to define the Per-Protocol Analysis Set (PPAS). For example:
 - Flu vaccines administered within 14 days pre or post each study vaccine, including the day of the study vaccination visit
 - Rotavirus vaccines administered within 14 days pre or post each study vaccination visit^b. Any vaccine other than study vaccines (vaccines non-described in the Protocol^c) within the 28 days (4 weeks) preceding or after the trial vaccination, including the day of the study vaccination visit
 - Immune globulins, blood or blood-derived products: used in the 3 months preceding the first blood draw and up to the last blood draw
 - Immunosuppressive therapy such as immune-suppressors, immune-modulators with immunosuppressive properties, long-term systemic corticosteroids therapy (prednisone or equivalent for more than 2 consecutive weeks) within past 3 months, anti-cancer chemotherapy, anti-proliferative drugs such as DNA synthesis inhibitors, or radiation therapy: used in the 6 months preceding the first trial vaccination, and up to the last blood draw.

^a Subject's parents will be required to document all medications received in the Diary Cards. The sites will focus on only recording the medications belonging to the 3 categories in the other source documents.

^b Subjects from Finland, Sweden and Poland can receive rotavirus vaccine concomitantly with study vaccinations at V1 and V2

^c if for any reason a study vaccine (PCV10, or PCV13 and/or Hexyon®/Hexacima®) is not administered concomitantly with investigation/control meningococcal vaccine, an interval of 4 weeks between this vaccination prior or following the investigational/control vaccine must be respected, otherwise, this vaccine administration out of the study will be considered as Category 2)

- Category 2 medications will be reported in the CRB during the study period up to the last blood draw.

In addition, the following vaccines should be recorded in the concomitant medication CRB as Category 2:

- Licensed Measles, Mumps and Rubella vaccines administered during the study participation (if MMR vaccination [including M-M-RVAXPRO®] occurred within the 28 days (4 weeks) preceding or after the trial vaccination visit, it will be used to define the PPAS definition)
- Licensed rotavirus vaccines received during the first year of life (if rotavirus vaccination occurred within the 14 days (2 weeks) preceding or after the trial vaccination visit, it will be used to define the PPAS definition)
- Hepatitis B Vaccine received before the inclusion in the study (if Hepatitis B vaccination occurred within the 28 days (4 weeks) preceding or after the trial vaccination visit, it will be used to define the PPAS definition)
- Category 3: Systemic (Oral or injectable) antibiotics, as they may interfere with bioassays used for antibody testing when taken before a blood draw. Antibiotics that the subject received within 72 hours preceding each visit for blood draw related to IMP assessment (meningococcal vaccines) and used to define the PPAS. Category 3 medications will be reported in the CRB for the period of 3 days (72 hours) before each blood draw.

Note: Topical antibiotics (Inhaled, otic, ophthalmic, nasal, etc.) should not be captured or reported.

The information reported in the CRB for each reported medication will be limited to:

- Trade name
- Rationale for the origin of prescription: Whether it was a prophylactic^a medication? Prophylactic medications will be recorded in the Action Taken section of the AE collection tables.
- Medication category (1, 2, or 3)
- Start and stop dates

Dosage and administration route, homeopathic medication, will not be recorded.

If the subject has received medications other than those listed in Categories 1, 2, and 3, the detailed information will be collected in the source documents only.

Medications given to treat an AE will be captured in the “Action Taken” section of the AE CRB only. No details will be recorded in the concomitant medication CRB unless the medication(s) received belongs to one of the prelisted categories.

^a Medication(s) prescribed for preventing AE occurrence (e.g. paracetamol to reduce the risk of fever)

7 Management of Samples

Blood samples for the assessment of antibody responses will be collected and subjects in Groups 1, 2, and 3 will provide blood samples for immunogenicity assessment as follows:

- at baseline (pre-primary vaccination 1, Day 0)
- 30 days (+21 days) after the 2nd dose of MenACYW conjugate vaccine / Nimenrix®
- prior to the 3rd dose (toddler dose) of MenACYW conjugate vaccine / Nimenrix®
- 30 days (+21 days) after the 3rd dose (toddler dose) of MenACYW conjugate vaccine / Nimenrix®

Subjects in Group 4 will provide blood samples for immunogenicity assessment as follows:

- at baseline (pre-primary vaccination 1, Day 0)
- 30 days (+21 days) after the 3rd dose of MenACYW conjugate vaccine
- prior to the 4th dose (toddler dose) of MenACYW conjugate vaccine
- 30 days (+21 days) after the 4th dose (toddler dose) of MenACYW conjugate vaccine

See the Table of Study Procedures and [Section 5.1.3](#) for details of the sampling schedule.

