9.3.2.3.2 Reactogenicity (Solicited Reactions from Day 0 to Day 7 after Each Vaccination)

After each vaccination, subject’s parents / legally acceptable representatives will be provided with a diary card, a digital thermometer, and a flexible ruler, and will be instructed how to use them. The following items will be recorded by the subjects in the diary card on the day of vaccination and for the next 7 days (ie, D0 to D07) until resolution:

- Daily temperature, with the route by which it was taken
- Daily measurement or intensity grade of all other solicited injection site and systemic reactions
- Action taken for each event (eg, medication)

The action(s) taken by the parent / legally acceptable representative to treat and/or manage any **solicited reactions** will be classified in the CRB using the following list (all applicable items should be checked):

- None
- Medication
- Health care provider contact
- Hospitalized

- Discontinuation of study vaccination

Parents / legally acceptable representatives will be contacted by telephone 8 days after each vaccination to remind them to record all safety information in the diary card.

If the timing of the telephone call should fall on a weekend or a holiday, the call should be made on the next business day. If contact is not made on the designated day, study staff will continue calling until contact is made. Every telephone attempt and its outcome will be documented in the source document.

Table 9.4 and **Table 9.5** present, respectively, the injection site reactions and systemic reactions that are prelisted in the diary cards and CRB, together with the intensity scales.

Table 9.4: Solicited injection site reactions: terminology, definitions, and intensity scales

CRB term (MedDRA lowest level term [LLT])	Injection site tenderness	Injection site erythema	Injection site swelling
MedDRA preferred term	Injection site pain	Injection site erythema	Injection site swelling
Diary card term	Tenderness	Redness	Swelling
Definition	Pain when the injection site is touched or injected limb mobilized	Presence of a redness including the approximate point of needle entry	Swelling at or near the injection site Swelling or edema is caused by a fluid infiltration in tissue or cavity and, depending on the space available for the fluid to disperse, swelling may be either soft (typically) or firm (less typical) to touch and thus can be best described by looking at the size of the swelling

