- Grade 2: A type of adverse event that is usually alleviated with additional therapeutic intervention. The event interferes with usual activities of daily living, causing discomfort but poses no significant or permanent risk of harm to the research participant.
- Grade 3: A type of adverse event that interrupts usual activities of daily living, or significantly affects clinical status, or may require intensive therapeutic intervention.
- Whether the AE was related to the investigational product (for unsolicited systemic AEs)

The Investigator will assess the causal relationship between the AE and the investigational product as either “Not related” or “Related”, as described in [Section 9.3.2.3.5](#).

- Action taken for each AE (eg, medication)

The action(s) taken by the parent / legally acceptable representative to treat and/or manage any unsolicited AEs will be classified in the CRB using the following list (all applicable items should be checked):

- None
- Medication
- Health care provider contact
- Hospitalized
- Discontinuation of study vaccination
- Whether the AE was serious

For each SAE, the investigator will complete all seriousness criteria that apply (outcome, elapsed time, and relationship to study procedures)

- Whether the AE caused study discontinuation

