4.4.1.3 Other Safety Endpoints

4.4.1.3.1 Action Taken

This information will be summarized as collected, including missing observations. No derivation or imputation will be done.

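### Protocol 6.7 sends preventive medication into the Action Taken field, which 9.3.2.3.2 and 9.3.2.3.3 reserve for treating or managing an event, so the descriptive Medication percentages can mix the two

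*Protocol*

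**What the plan says.** Protocol 6.7 lists what is reported for each concomitant medication: trade name, category, start and stop dates, and an item on its purpose ("Rationale for the origin of prescription: Whether it was a prophylactic"). To that item it adds: "Prophylactic medications will be recorded in the Action Taken section of the AE collection tables". The footnote defines such drugs as "Medication(s) prescribed for preventing AE occurrence (e.g. paracetamol to reduce the risk of fever").

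Further down, the same section uses the same destination for treatment: "Medications given to treat an AE will be captured in the" Action Taken section, with a concomitant-medication entry as well if the drug falls in a prelisted category.

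The sections that define the field describe it differently. For solicited reactions, Protocol 9.3.2.3.2 has the CRB classify "The action(s) taken by the parent / legally acceptable representative to treat and/or manage any" solicited reactions. Protocol 9.3.2.3.3 reads: "The action(s) taken by the parent / legally acceptable representative to treat and/or manage any unsolicited AEs will be classified in the CRB". Both lists have one Medication option, with no subdivision by purpose.

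Action taken is a named element of the immediate, solicited, unsolicited and SAE endpoints (Protocol 9.3.2.2; SAP 5.1.5.2), and Protocol 12.1.3 plans a summary of solicited reactions by it. SAP 4.4.1.3.1 says of the field: "This information will be summarized as collected, including missing observations. No derivation or imputation will be done".

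**The concern.** A drug given to prevent fever is not an action taken in response to fever. If a child receives paracetamol around vaccination and later has any reaction, a site following 6.7 would tick Medication against that reaction even if nothing was given because of it. The tables would then show a medicated reaction.

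How often reactions led to medication is part of how reactogenicity is described in this trial. The protocol recognises that these drugs matter: Category 1 covers medications with potential impact on the safety evaluation ("For example, antipyretics, analgesics, non-steroidal anti-inflammatory drugs (NSAIDs), systemic corticosteroids (therapy duration less than 2 weeks), and other immune modulators"). A field that records treatment at one site and treatment plus prevention at another does not have a single meaning, and the SAP contains no step that restores one.

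**Working it through.** The plan gives no figure to reproduce: neither a rate of prophylactic use nor a rate of treated reactions. The check is therefore mainly a comparison of the texts.

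| Question | Protocol 6.7 | Protocol 9.3.2.3.2 and 9.3.2.3.3 |
|---|---|---|
| Drug given to treat an event | Action Taken | Action Taken, Medication |
| Drug given to prevent an event | Action Taken | Outside the definition (treat and/or manage) |
| Can the field show the purpose? | Not in Action Taken; yes on the concomitant-medication form | No, one Medication option |

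1. **Conflict.** The second row gives two incompatible instructions for one field.
2. **Direction.** Following 6.7 adds Medication ticks and removes none. A reactor who had both prophylaxis and treatment is ticked once under either reading. A child with prophylaxis and no reaction has no event record, so adds nothing. Any error in the Medication percentage is therefore upward.
3. **Size.** Let t be the share of reactors truly treated with medication, and q the share of the remaining reactors whose preventive dose is ticked against the reaction. Then the reported share is t + q(1 − t). All values of t and q below are assumptions.

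| t | q = 0 | q = 10% | q = 30% | q = 50% |
|---|---|---|---|---|
| 20% | 20% | 0.20 + 0.80 × 0.10 = 28% | 0.20 + 0.80 × 0.30 = 44% | 0.20 + 0.80 × 0.50 = 60% |
| 50% | 50% | 0.50 + 0.50 × 0.10 = 55% | 0.50 + 0.50 × 0.30 = 65% | 0.50 + 0.50 × 0.50 = 75% |

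   The q = 0 column is what results if every site follows 9.3.2.3.2 and 9.3.2.3.3. The table shows how the mechanism works and does not estimate its effect in this trial.
4. **Can the uses be separated later?** Antipyretics and analgesics are Category 1, reported in the CRB from first vaccination through the follow-up after each dose, with the prophylactic item and dates. The raw material therefore exists. However, no output in the SAP uses the prophylactic item. The documents describe no link from a ticked action to a particular medication record. The form lists dates but no times, so dates alone cannot order a dose and an onset on the same day. SAP 5.7 also reports that the medication category fields were inactivated and the drugs coded with WHODrug; it says nothing about the prophylactic item.

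**The case against.** The best defence is that little follows from one misplaced sentence. Sections 9.3.2.3.2 and 9.3.2.3.3 are where sites look for how to complete the field, and they limit it to treating or managing the event. The CRF Completion Instructions, which are not among the documents reviewed, may settle the matter. Safety is an observational, descriptive objective. Action taken enters no test and defines no analysis set, and Category 1 medications are expressly kept out of the PPAS definition. Those statements about materiality stand. They do not remove the conflict, because 6.7 is itself a recording instruction in force.

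A reader might also infer more than the documents support:

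- **That the results do overstate medication use.** This requires sites to have followed 6.7 rather than the 9.3.2.3 sections. The documents do not show which they followed.
- **That prevention and treatment cannot be told apart afterwards, or that prophylaxis is lost when no reaction follows.** The Category 1 entry, with indicator and dates, is required whether or not an AE occurs.
- **That group comparisons are biased.** Groups 1 and 2 are randomised with stratification by center (Protocol 6.5), and their meningococcal vaccines are given in a modified double-blind manner (6.4) under the same recording rule, so that comparison is little affected. Groups 3 and 4 are in other countries, so national habits could show in a descriptive contrast with Groups 1 and 2. That contrast is already non-randomised, none is tested, and the documents give no evidence that prophylaxis rates differ.

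**Conclusion.** The inconsistency is established. Protocol 6.7 assigns preventive medication to a field that 9.3.2.3.2 and 9.3.2.3.3 define as treatment or management, and SAP 4.4.1.3.1 passes the field through unsplit. Where 6.7 was followed literally, the Medication percentages can mix prevention with treatment and can only be too high. The amount cannot be computed from the documents and may be zero.

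The upward direction assumes only that sites ticked Medication for preventive doses in addition to true treatment. The effect is confined to descriptive safety summaries; neither the primary objective nor Secondary Objective 1 is touched. The point merits correction because the recording rule contradicts the field's own definition and the repair uses items already listed for collection. This concerns recording and reporting only, not whether prophylaxis should be given.

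**What to change.** **Protocol and CRF instructions.** Reconcile 6.7 with 9.3.2.3.2 and 9.3.2.3.3. Prophylactic medication stays on the concomitant-medication form with its existing indicator and start and stop dates. Medication under Action Taken is reserved for medication given to treat or manage the event. A rule based purely on starting after onset would be narrower than the protocol's definition, since a drug begun earlier may be continued to manage the event.

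**SAP.** The SAP already describes vaccination and safety follow-up in the past tense, so a protocol change will not alter recorded data. Add to 4.4.1.3.1 a rule that uses the prophylactic indicator, dates and WHODrug coding, not the inactivated category fields, to do one of the following:

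- report action-taken Medication excluding reactions whose only medication was prophylactic; or
- report prophylactic-only and treatment use on separate lines.

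Add a table footnote where the two cannot be separated, for example where no matching medication record exists or the indicator is missing. First confirm that the indicator was kept when the category fields were inactivated.

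**Cost.** One protocol sentence, one line in the CRF instructions, and one SAP rule with a footnote. No new data items are needed, but the matching of medication records to reactions has to be programmed.

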7.1 Sample Collection

A total of 4 blood samples will be collected from all subjects during their study participation by staff experienced in blood collection in a pediatric population.

The Investigators should comply with European Regulation on the maximum amount of blood drawn that could be collected at any one time from children. According to European Regulation, the amount of blood drawn at any one time from the children in the study must not exceed 1% of their total blood volume (refer to Operating Guidelines for more detailed instructions) [\(48\)](#).

At Visit 1, 2 or 3 mL of blood will be collected depending on the subject's weight at the time of study visit; at Visit 3, 3 or 4 mL of blood will be collected depending on the subject's weight at the time of study visit; and at Visits 4 and 5, 5 mL (or 6 mL) of blood will be collected from subjects in Groups 1, 2, and 3. For subjects in Group 4, 2 or 3 mL of blood will be collected at Visit 1 depending on the subject's weight at the time of study visit, 3 or 4 mL of blood will be collected at Visit 4 depending on the subject's weight at the time of study visit, and 5 mL (or 6 mL) of blood will be collected at Visits 5 and 6 in tubes provided by or recommended by the Sponsor.

For Groups 1, 2, and 3, the blood sample volume indicated will be taken from all subjects and those subjects included in a subset to assess the antibody response to meningococcal serogroups (A, C, W, and Y) measured by rSBA assay in addition to hSBA assay at Visits 1 and 3. At Visits 4 and 5, blood sample volume of 5 mL will be taken from all subjects except subjects included in the rSBA subset. Blood sample volume of 6 mL will be taken from subjects included in the rSBA subset.

For Group 4, the blood sample volume indicated will be taken from all subjects and those subjects included in a subset to assess the antibody response to meningococcal serogroups (A, C, W, and

Y) measured by rSBA assay in addition to hSBA assay at Visits 1 and 4. At Visits 5 and 6, blood sample volume of 5 mL will be taken from all subjects except subjects included in the rSBA subset. Blood sample volume of 6 mL will be taken from subjects included in the rSBA subset.

Immediately prior to the blood draw, the staff member performing the procedure will verify the subject's identity; will write the assigned subject's number on the pre-printed label that contains that subject's number and the sampling stage; and will attach the label to the tube. Blood is to be taken from the limb opposite to the one that will be used for vaccination.

